2. EXTERNAL IRB REVIEW HISTORY*

N/A

3. PRIOR APPROVALS:

All necessary approvals will be obtained prior to commencing the research.

Conflict of Interest (COI): We will adhere to the mitigation plan developed by the campus COI Committee which includes the following:

- 1. [name] will not be involved in enrolling or consenting subjects in this study.
- 2. The patient consent form shall include the following

 The study is being paid for by the National Institutes of Health. UMMS and Q2i are
 - The study is being paid for by the National Institutes of Health. UMMS and Q2i are collaborators in this project. Any assessments or interventions that are developed as part of this project will be jointly owned by UMMS and Q2i. Both organizations and the participating scientists could potentially earn money from selling the assessments and interventions developed during this study. [name], the Principal Investigator on this study, is a faculty member at UMMS. He also is an unpaid advisor to Q2i. [name] does not get paid for the work he does for Q2i.
- 3. [name] will disclose his relationship with the company in publications and presentations related to the product.
- 4. During the course of the study, [name] cannot serve as a scientific officer, director or board member of the company. The Q2i website will prominently indicate that [name] is an unpaid advisor to Q2i.
- 5. [name] will not directly analyze the data. Instead, the study statistician or other qualified personnel will analyze the data.
- 6. [name] will be required to abstain from the purchase or acceptance of options for company stock during the study. This term shall also apply to immediate family members. The foregoing restrictions shall remain in effect for a period of one year after the end of the study.
- 7. [name] will notify the COI Committee should his financial interest or the nature of his collaboration with Q2i.

UMMS Data Core request: Electronic Health Record Integration: This is a Fast-Track STTR. This means the NIH will fund Phase 1 first, then make a decision about whether to fund Phase 2 after reviewing the progress report from Phase 1. The OARSCM software being developed with this grant will ultimately be integrated with the UMMHC EHR (Epic). However, this is not anticipated to happen in the Phase 1 part of the study. We will be submitting our data request to the UMMS Data Core, but we do not anticipate full approval of integration and resolution of data sharing and security until AFTER Phase 1 is complete. We will submit additional materials to the IRB as needed once Phase 1 is complete and the path for integration is cleared through UMMS Data Core.

4. OBJECTIVES*

The Specific Aims for Phase 2 have been modified from the original submission with approval from the program officer at NIDA. Updated Aims are as follows:

Phase 1, Aim 1: To develop the OARS+CM platform. User-centered design principles will be employed to enhance the existing OARS software to produce OARS+CM. This will culminate in a proof-of-concept study of up to 20 individuals with OUD and their providers/clinicians whose feedback and experiences will be used to iteratively improve the interface and features. The usability criterion will be reached when \geq 3 participants in a row are able to use the program without staff assistance (with on-device support if needed, as intended) and no more substantive improvements are needed. We will also assess acceptability, and rates of treatment initiation and adherence (attending therapy, drug urine/saliva tests).

Phase 2, Aim 1: To assess the efficacy of OARS+CM in promoting MOUD treatment initiation. Using a randomized controlled trial (N=102 randomized), the efficacy of the OARS+CM (n=51) in promoting MAT initiation will be tested against TAU with MyMAT (an educational mobile app) (n=51).

H1: OARS+CM will result in greater MOUD treatment initiation from acute care settings than TAU with MyMAT.

Phase 2, Aim 2: To assess efficacy of OARS+CM in promoting transition from MOUD Initiation to maintenance.

H2: OARS+CM will result in greater rates of sustained abstinence for 6 months after the index visit.

H3: MOUD therapy attendance will be increased such that OARS+CM >TAU with MyMAT.

Phase 2, Aim 3: To evaluate costs. Exploratory data on cost-effectiveness, cost avoidance and cost savings through reduced acute care visits between conditions will be collected and analyzed.

This submission is currently seeking approval for Phase 2 following successful completion of Phase 1, as the NIH will only fund Phase 2 if Phase 1 is successful. All materials for Phase 2 in this submission outline what has occurred since Phase 1 was completed successfully. Any changes to Phase 2 material have been revised and are being submitted to the IRB as a modification for review and approval when appropriate.

5. BACKGROUND*

See grant: "RESEARCH STRATEGY" (p.2-4) for details. The Procedures for Phase 2 have been modified from the original submission. Updated Procedures are as follows:

Procedures

Screening, recruitment, eligibility and training procedures are in C.2.1 and the Eligibility criteria document.

Randomization will occur following determination of eligibility using an urn procedure and stratifying on 1) other (than opioid) substance use disorder no/yes, 2) gender/sex, 3) race/ethnicity.

TAU with MyMAT (n = 51). In the acute care setting, the Behavioral Health Service run by Drs. [name] and [name] provides SBIRT for substance use disorders, including OUD. They provide SBIRT as part of TAU, including, when possible, warm handoff contact with outpatient MOUD treatment that includes a scheduled outpatient appointment, optimally within 48 hours of the ED visit. Patients randomized to this group will also receive MyMAT, a mobile application with opioid treatment educational content, as an attention control measure against OARS+CM. TAU outpatient suboxone treatment consists of urine toxicology screening, group/individual therapy, and MOUD prescription continent on drugnegative (except cannabis, which is legal in MA) urine toxicology. Treatment visits are typically, weekly in weeks 1-4 and then taper over time, to every other week in weeks 5-8, and monthly in weeks 9-12 and thereafter. Nonadherence can lead to increased frequency/intensity of therapy and urine toxicology until the patient stabilizes. If increased frequency/intensity is unsuccessful, patients may be referred to detoxification and subsequently re-admitted to outpatient care when appropriate.

OARS+CM (n = 51) patients will receive the same TAU procedures described above. They will also earn chances for prizes, with the same targeted behaviors, escalation of chances for prizes for each targeted behavior in a row, and reset criteria described. Briefly, for scheduling a MOUD treatment intake patients will earn 1 guaranteed prize of \$5 and for completing their MOUD treatment intake patients will earn 1 guaranteed prize of \$20. After intake, patients will earn chances to win prizes for each targeted behavior completed. Chances for prizes will start at 2 and then will increase by 2 chances with documentation of each targeted behavior in a row up to a maximum of 10 draws/targeted behavior. With 38 targeted behaviors (schedule MOUD intake, complete intake, 12 opioid-negative urine toxicology/week over 12 weeks plus bonuses for cocaine-negative tests, and 12 group/individual therapy/week over 12 weeks), patients can earn up to 252 chances for prizes during the 12-week RCT.

6. INCLUSION AND EXCLUSION CRITERIA*

Inclusion and Exclusion Criteria: See grant: "HUMAN PARTICIPANTS PROTECTION" (p.17) for details. The Overall Study Design, Study Population and Randomization, and Interventions for Phase 2 have been modified from the original submission. Updated Overall Study Design, Study Population and Randomization, and Interventions are as follows:

Overall Study Design: This Fast-Track STTR includes a small proof of concept pilot study followed by a randomized controlled trial (RCT) with two conditions: 1) treatment as usual (TAU) with MyMAT, and 2) the OARS + CM. This study will use recruitment and study enrollment procedures successful in our prior SUD research (refer to Biosketches). Participants will be individuals with OUD presenting to acute care settings. They will complete a screening survey to assess for minimal eligibility criteria and confirm their interest. Once confirmed, research staff will obtain written informed consent and enrolled in the study. Participants will be randomized to one of two conditions described above. The study period begins at enrollment during their index acute care visit. Follow-up surveys and tracking through the mobile application (OARS+CM) and review of all relevant healthcare records will occur at 1, 3, and 6 months after enrollment. For scientific rigor, biochemical verification of abstinence from opioids

will be obtained from outpatient treatment records. Self-reported use will also be obtained through structured follow-up assessments.

Study Population and Randomization: We will randomly assign N=102 individuals with OUD meeting minimal eligibility criteria to one of two conditions using REDCap, allocated 1:1 to the two conditions.

Interventions:

Group A: TAU with MyMAT. For TAU participants, the usual care provided to individuals with OUD at the UMass University and Memorial hospitals will be provided. This typically consists of (1) medical stabilization and treatment, as needed; (2) brief counseling and referral to treatment by a social worker or other behavioral health provider, which includes providing a tailored referral list; and (3) when the patient is interested and treatment facility available, a "warm handoff" comprised of contact with the outpatient provider and transportation directly to the facility or a scheduled intake appointment within 48 hours, when feasible. TAU participants will also receive MyMAT, a mobile application with opioid treatment educational content, as an attention control measure against OARS+CM.

Group B: OARS+CM. Participants assigned to OARS+CM will receive the same treatment as in the TAU condition but with the enhancement of the CM features, described in detail in Section C.2.1, Proof-of-concept testing for usability section.

Table 1: Eligibility criteria						
Inclusion	Exclusion					
→ >= 18 years old	 Persistent altered mental status (not alert, not oriented, psychotic). 					
◆ Presenting for acute care at UMass University and Memorial hospitals, including EDs, inpatient medical units, inpatient behavioral health units, or community acute care partners for opioid addiction related health complaints, including opioid overdose, opioid related medical consequences, opioid intoxication or withdrawal syndromes, and/or seeking help for OUD	Patient declines referral to UMass Bridging MAT Clinic, to CleanSlate Addiction Treatment Center, to SaVida Health, to Eleanor Health, or to Spectrum Health Systems for MOUD.					
 Presence of a current DSM-V opioid use disorder (OUD), mild to severe 	 Not interested or willing to participate in MOUD treatment 					
 Medically appropriate for outpatient MOUD treatment, as judged by the 	 Unwilling to use the OARS+CM app (if assigned) 					
treating clinician and behavioral health consultant or toxicologist working with the patient clinically	 Does not have access to their own smartphone with at least iOS 7.1 or Android 4.2, the minimal technology required to run the app, or not willing to access clinic- dedicated computer to access the program 					

	Currently a UMMS student			
 Treatment provider of patient who 	 Prisoner or currently in state custody or 			
consented to participate	pending legal action that might lead to			
	imprisonment			
	 Cannot paraphrase the study requirements 			
	 No reliable telephone access 			
	 Does not read or speak English 			
	Does not reside in the central MA region			
	Already enrolled into the trial			

7. STUDY-WIDE NUMBER OF SUBJECTS*

N/A

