- 2a. Patient participants will complete a short survey on the iPad and a 20-30-minute interview-assessment during their hospital visit. Patient will provide their general impressions of the OARSCM mobile application (e.g., perceived appropriateness, acceptability, and feasibility), as well as any identified barriers or weaknesses. It will not interfere with care.
- 2b. At a later time, all clinicians (dyad or not) will complete an in-person or virtual interview to provide their general impressions of the OARSCM provider portal (e.g., perceived appropriateness, acceptability and feasibility), as well as any identified barriers or weaknesses. This clinician interview will occur outside of the acute care and outpatient visit to not interfere with any patient care. All interviews will be audio recorded with verbal consent.
- 3. If a dyad clinician elects to withdraw from the study but the patient chooses to remain enrolled, a research assistant will be responsible for inputting the patient data into OARSCM as to not interrupt the patient's ability to earn prizes. We would also not obtain the clinician's user testing data.
- 4. Patient will be connected to a community based Suboxone treatment provider, the UMass Bridging Clinic, the CleanSlate Addiction Treatment Center, SaVida Health, or Spectrum Health Systems and schedule an intake appointment. Patient will receive standard MAT treatment and will use the OARSCM mobile application to track their progress in treatment. To use the OARSCM mobile application to track their progress in treatment, patient will enter their name (first and last), email address, DOB and cell phone number when available into the application to create an account. Patient will have the option to journal free text entries about how they are thinking and feeling throughout treatment. Patient will have the opportunity to earn prizes for engaging the OARSCM program throughout treatment. Engagement in treatment is measured by scheduling and attending treatment appointments as well as urinary tox results, all of which is entered into the OARSCM program by the MAT provider using the provider portal. See "APPENDIX" for screenshots of patient application and provider portal.

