5. Patient will not receive any follow up calls after the hospital visit but will have their use of the OARSCM mobile application and engagement with treatment as tracked by the OARSCM mobile application monitored for 4 weeks. Participation in this study will last about 4 weeks once the patient has started MAT treatment. After these 4 weeks, the participants will be informed that their 4-week participation has now ended and that we appreciate their participation. They will also be informed that new information related to their appointments, appointment attendance, appointment engagement and tox results will not be entered into their OARSCM mobile application profile. However, they will be able to view this DATA that had been previously entered throughout the 4-weeks. They will continue to have access to their OARSCM mobile application account in order to use their unredeemed Spins, Prizes, and eGift cards for a short time. During enrollment, patient participants will be given a handout on how to uninstall the application if they no longer want the application on their smart phone after participation. See grant: "RESEARCH STRATEGY" (p. 8). See grant: "APPENDIX" for screenshot of patient notification that their 4-week participation has now ended and handout of how to uninstall the mobile application.

Phase 2: Aims 1 and 2 (Efficacy of OARSCM): 102 patients randomized to 1 of 2 groups If the patient agrees to participate:

- 1. Participants (acute care patients who meet eligibility criteria and complete consent process, see section 30. Consent Process) will be randomized to either TAU (with MyMAT) or OARS mobile application plus contingency management (OARSCM).
- 2. Participants will complete an interview assessment during their current medical visit. It takes about 20-30 minutes to complete. They will be asked to provide a urine sample. It will not interfere with their care.
- 3. Participants will be provided a warm handoff to a community-based MOUD treatment provider. All participants will be eligible to receive standard MOUD treatment per treatment as usual at the site they are referred to. If they are randomized to OARSCM, they will use the mobile application to track treatment progress and have the potential to earn prizes for engaging with the application throughout treatment.

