- 4. Participants will receive a welcome call at 1-week post-enrollment. This call will welcome participants to the study and provide an opportunity to answer any questions they may have about participation as well as ensure they are not having any issues with study mobile applications. This call will take about 5 minutes.
- 5. They will complete 3 follow-up telephone calls to find out how they are doing. The calls will focus on their substance use, especially opioid use, treatment engagement, healthcare visits, health, and well-being. These calls will take about 20 30 minutes to complete. The calls will occur at 1, 3, and 6 months after the enrollment date.
- 6. The researchers will review the participants' healthcare records, including the Massachusetts Prescription Monitoring Program's EHR-integrated tool MassPAT that provides information on participant's prescriptions for MOUD through the 6 months after enrollment. We will review the

healthcare record for all participants and will only be viewing the MassPAT record for participants who do not have urine toxicity results at their outpatient MOUD provider at the 1, 3, and 6-month follow up time points. MassPAT will be used to determine if a participant is still engaging in treatment during these follow-up time points if the participant cannot be reached for their follow-up interviews or if they have stopped attending appointments at their study clinic site and have not requested to leave the study.

- 7. We will be seeking to collect information from medical providers or records outside of the UMMS system (a substance use treatment provider in the community that doesn't have a UMMS connection) and will require a signature on a Release of Medical Information with designated treatment facilities identified
- 8. The researchers will review publicly available databases, like the participants' state's vital statistics registry (a document created by the state that tracks important health indicators, like births, deaths, and cause of death). See grant: "RESEARCH STRATEGY" (p.8-13) for details.

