23. RESOURCES AVAILABLE

Research Personnel. Investigators and key personnel will have undergone mandatory education in human research participants' protection. Educational systems are in place to ensure that all research staff have been through such training and are approved by the IRB Human Subjects department. The responsibilities of investigators and research personnel are as follows:

Principal Investigator. The Principal Investigator will be responsible for overall project governance at UMass, leadership of the Project Team at UMass, protocol development, informing the data analytic plan, and dissemination efforts through professional presentations and peer reviewed journal publications

Co-Investigator. The Co-Investigators will be responsible for collaboration with other MOUD providers in the region and overseeing communication between research staff and community MOUD providers. Other responsibilities include overseeing contingency

management plan development and implementation and advising the team on data management and quality assurance protocols.

Project Manager. The Project Manager will be responsible for managing daily operations of recruitment and enrollment including training and supervising the research assistants. They will manage all IRB related submissions, amendments, and reporting.

Research Assistant(s). The research assistant(s) will be responsible for reviewing the electronic health record dashboard each shift and documenting potentially eligible patients on a Screening Log. They will be responsible for enrolling participants conducting interviews and completing telephone outcome assessment services for the stud(ies).

Software Engineer. The software engineer will be responsible for programming and managing the OARSCM mobile application and ensuring all data is flowing correctly between the mobile application and the secure server. They will have access to identified data within the Q2i OARSCM secure server at AWS. This data will include the patient's name (first and last), DOB, email address, cell phone number, urine toxicology results, and attendance in treatment. PHI will be directly entered into the mobile application. Q2i will have access to the server via secure shell terminal sessions. The OARSCM mobile application does not store PII/PHI locally on the device.

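### No common data source is set for intake and attendance, while app tracking listed as follow-up data exists only in the OARS+CM arm

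*Protocol*

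**What the plan says.** **App tracking as follow-up data.** Protocol Section 6, Overall Study Design: "Follow-up surveys and tracking through the mobile application (OARS+CM) and review of all relevant healthcare records will occur at 1, 3, and 6 months". The sentence after it assigns biochemical verification of opioid abstinence to outpatient treatment records.

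**One arm only.** Protocol Section 11, Phase 2 step 3: "If they are randomized to OARSCM, they will use the mobile application to track treatment progress". For the control arm, Section 6 says: "TAU participants will also receive MyMAT, a mobile application with opioid treatment educational content, as an attention control measure against OARS+CM". No tracking function is described for MyMAT.

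**What the app system holds.** Section 23 (Software Engineer) lists "urine toxicology results, and attendance in treatment" among the data on the OARSCM server. The Phase 1 procedures in Section 11 say that scheduling, attendance and urine results are "all of which is entered into the OARSCM program by the MAT provider using the provider portal". In Phase 2, Section 5 makes prizes depend on the record: chances "will increase by 2 chances with documentation of each targeted behavior in a row", and scheduling and completing the intake each earn a prize.

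**Sources shared by both arms.** Section 11 gives healthcare record review for all participants, calls at 1, 3 and 6 months that cover treatment engagement, and MassPAT for participants who lack urine results at their clinic. Collecting records from outside providers "will require a signature on a Release of Medical Information with designated treatment facilities identified". The assessment table lists monitoring of intake completion, weekly monitoring of attendance and toxicology, and study urine tests. None of these rows is limited to one arm, and the two monitoring rows name no source.

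**Outcomes.** The SAP's primary outcomes are the proportions who schedule and who complete the intake. The main Aim 2 outcomes are the percentage of opioid-free tests and the percentage of sessions attended. No source, order of sources or denominator is given for any of them.

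**The concern.** The events that earn prizes in OARS+CM are also the trial's outcome events. In that arm there is a system built to document them and a reason to do so. In TAU with MyMAT there is neither. If an entry in the app or portal can score an outcome that the shared sources missed, the same behaviour can be counted in one arm and not in the other.

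The outcome at stake is the primary one. Protocol Section 32 says that the data will support a 510(k) submission, so a difference that partly reflects documentation would be hard to defend. Section 23 has the research assistants both enrol participants and carry out the outcome calls, and no masked abstraction of outcomes is stated.

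**Working it through.** **1. The plan's own figure.** The SAP claims power above 0.80 for three pairwise comparisons with 50 per group, from a 35% control rate and increases of 25% and 50%. With the pooled normal approximation:

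| Reading of the increases | Test | TAU v OARS | TAU v OARS+CM | OARS v OARS+CM |
|---|---|---|---|---|
| Absolute (35/60/85%) | two-sided | 0.713 | >0.999 | 0.809 |
| Absolute (35/60/85%) | one-sided | 0.812 | >0.999 | 0.885 |
| Relative (35/43.75/52.5%) | two-sided | 0.143 | 0.421 | 0.138 |

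The claim is reproduced only with absolute increases and a one-sided test. It belongs to a superseded three-arm design and does not decide this point. Only the 35% is carried forward.

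**2. Inputs for the capture check.** 51 per arm (Protocol Section 25); 35% initiation (SAP, Sample size justification), taken as true in both arms; two-sided 0.05 (the SAP gives 0.05 but not the sidedness). Two inputs are assumptions: OARS+CM captures every start, and TAU captures a fraction s after all shared sources have been used. The documents give no value for s.

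**3. Formulas.** Observed TAU rate = 0.35 × s. Spurious difference = 0.35 × (1 − s). With proportions a (TAU) and b (OARS+CM) and pooled proportion p, z = (b − a) / √[2p(1 − p)/51], rejecting when |z| ≥ 1.96. The rejection probability is the exact sum over all pairs of counts from Binomial(51, 0.35s) and Binomial(51, 0.35).

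**4. Results.** Expected true TAU starts are 51 × 0.35 = 17.85.

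| TAU starts missed | Number missed | Observed TAU rate | Spurious difference | Rejection, two-sided | Rejection favouring OARS+CM |
|---|---|---|---|---|---|
| 0% | 0 | 35.0% | 0 | 5.1% | 2.5% |
| 10% | 1.8 | 31.5% | 3.5 points | 6.7% | 5.7% |
| 20% | 3.6 | 28.0% | 7.0 points | 11.8% | 11.5% |
| 30% | 5.4 | 24.5% | 10.5 points | 21.4% | 21.3% |

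A higher true rate makes the same fractional loss matter more. At an assumed 60% in both arms, two-sided rejection is 5.5% with no loss and 10.4%, 25.1% and 47.7% at 10%, 20% and 30% loss.

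A real effect would be exaggerated too. On the relative reading, 52.5% v 35% is 17.5 points. A 10% loss in TAU makes it 52.5 − 31.5 = 21.0 points, and a 20% loss 52.5 − 28.0 = 24.5 points.

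**5. Aim 2.** These outcomes are percentages. If the denominator is a fixed number of expected sessions or tests and an undocumented event counts as a failure, fuller capture can only raise the percentage. If the denominator is the documented events, fuller capture also adds positive tests and missed sessions and can lower it. The sign is therefore not determined. The room for unequal capture looks wider here than for initiation. Section 5 sets weekly targets over 12 weeks for OARS+CM while usual visits taper after week 4, and MassPAT shows prescriptions, not therapy sessions.

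**The case against.** A reader might infer that usual care has only charts and released records, that app entries will score outcomes, and that the trial is therefore biased toward OARS+CM. The documents do not support that.

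- MassPAT, the calls, the study urine tests and the monitoring rows apply to both arms. The release for outside records is also not specific to one arm.
- No text says that app entries score an outcome. The Section 23 wording describes a software engineer's data access.
- Biochemical verification of abstinence is assigned to outpatient records, which weakens the concern for toxicology.
- The portal-entry description is Phase 1 text; its use in Phase 2 is inferred. Section 24 adds that in Phase 1 the provider could also see the same data in the EHR, so events held only in the app may be few.
- Intake scheduling is part of the warm handoff in both arms.
- Section 10 leaves the endpoints to the grant, which may define sources and was not available here.

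All of this stands, and it reduces the point to a possibility. It does not remove it. Shared sources do not cancel an extra source in one arm unless a rule excludes it, and neither document has such a rule. MassPAT is viewed only when clinic urine results are missing, and it cannot show scheduling or sessions. Calls are self-report and can be missed.

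**Conclusion.** The concern holds as a gap in outcome definition. A source available in one arm is listed as follow-up data, and nothing states which source defines scheduling, intake completion or attendance, or bars app entries from counting. Differential capture is permitted by the plan, not shown to occur.

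For initiation, any such difference would favour OARS+CM. Under the stated assumptions (35% true initiation in both arms, full capture in OARS+CM), the false-positive rate moves from about 5% to 6.7% at 10% loss and 21.4% at 30%. At 10% fewer than two TAU starts are missed and the effect is small. These loss rates are illustrations and apply after every shared source has been used. For the Aim 2 percentages, no direction can be claimed until the denominator is fixed.

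**What to change.** In Protocol Section 6 (Overall Study Design) and in the SAP paragraphs on Primary Aim 1 and Aim 2, state that these outcomes are scored in both arms from the same sources in the same order:

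- scheduling: the acute-care handoff record;
- intake completion, attendance and toxicology: outpatient clinic records;
- MassPAT: backup evidence of treatment, under one rule for both arms.

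Limiting the sources to clinic records would be too narrow, because it would drop MassPAT and the acute-care record of scheduling.

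Abstract with one form, without reference to arm where existing staffing allows. Use app and portal data only to run the prizes, to describe app use or in a sensitivity analysis. State the denominators of the Aim 2 percentages, and report source completeness by arm.

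The cost is mainly wording, since record review of all participants is already planned. Masked abstraction needs someone who did not enrol the participant, hence the staffing condition. The small downside is that events logged only in the app do not count in the main analysis.
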